**PI: [name], Ph.D**

### **Purpose of the Study**

The purpose of the present study is to determine cross-sectional relationships between macular pigment optical density (MPOD) and visual performance in glaucoma. Also, to determine the effect of lutein, zeaxanthin, and mesozeaxanthin supplementation on MPOD and visual performance in glaucoma patients.

### **Background & Significance**

Neurodegeneration of the optic nerve and associated ganglion cell death in glaucoma leads to several well-characterized losses in visual function, most notably progressive peripheral visual field loss (see, e.g., Weinreb et al. 2014). Several recent studies (Amanullah et al. 2017; Siah et al. 2017; Wang et al. 2017; Bambo et al. 2016) have characterized significant visual function deficits in glaucoma patients that may be more sensitive indicators of disease than classical visual field loss, including compromised CS, increased disability glare (DG) and protracted dark adaptation (DA).

Given the available evidence, it appears that visual function, if assessed carefully, is a reliable indicator of ocular health and / or disease state. It follows that an improvement in visual function would be indicative of an improvement in ocular health. Although improvement of visual function is not typically seen in ocular disease, there is recent evidence to suggest that visual performance and associated progression of ocular disease may actually be modifiable via nutritional strategies and dietary modification (in age-related macular degeneration [AMD]; Nolan et al. 2017). Because much of the structural damage in glaucoma is associated with increased ocular inflammation (see, e.g., Vohra et al. 2013), local anti-inflammatory action may extend or improve good visual performance, and perhaps even hold the progression of the disease at bay. Given their exceptional anti-inflammatory activity and potential for rich deposition in the retina, the macular carotenoids lutein (L), zeaxanthin (Z), and mesozeaxanthin (MZ) may hold promise for this strategy. Indeed, a recent cross-sectional study (Siah et al. 2017) of the relationship between macular carotenoid level and visual performance in glaucoma patients found that those patients with low levels were significantly more likely to experience problems with glare – and were also more likely to have greater ganglion cell loss.

L and Z are diet-derived, yellow-orange colored carotenoids obtained primarily from leafy-green vegetables (Sommerburg et al., 1998). L and Z are not synthesized by the body, and therefore must be obtained via dietary means; those who have diets rich in leafy greens, or supplement with sufficient L and Z tend to maintain and accumulate higher blood and tissue concentrations (Ciulla et al., 2001; Bone et al., 2003). One of the conspicuous features of L and Z is their specific accumulation in the macular retina (Snodderly et al., 1984b), where they can reach extremely high concentrations – values as high as 1.50 log optical density near the foveal center are not uncommon (e.g., Hammond et al. 1997); it is also not uncommon to see concentrations in the fovea that exceed 10,000 times that seen in the blood (Bone et al. 1993). Once deposited in the retina, some of the L is converted to a stereoisomeric form of zeaxanthin, called mesozeaxanthin (MZ; Neuringer et al. 2004). Although rare, MZ has been shown to exist in nature, and indeed in the human food chain - its presence has been recently verified in salmon, trout, and sardine skin, and also trout flesh (Nolan et al., 2014). Importantly, MZ has been shown to be readily deposited in the retina when taken in supplement form (Loughman et al., 2012). The accumulation of these three carotenoids in the macula yields a yellowish-orange coloration, classically known to ophthalmologists as the “macula lutea” (“yellow spot”; first noted by Buzzi, 1782). Today, this collective pigmentation is commonly referred to as macular pigment (MP; Wald, 1945), with concentrations typically expressed in terms of optical density (MPOD). Xanthophyll carotenoids such as L, Z, and MZ are especially potent antioxidants (Krinsky et al., 2003). Via a process called triplet excitation transfer (Ruban et al., 2002), L, Z, and MZ can regenerate to repeatedly “quench”

**PI: [name], Ph.D**

the energy of singlet oxygen. This makes them capable of long-term accumulation in target tissues such as the retina, where, in the absence of excessive oxidative or inflammatory stress (e.g. smoking, or systemic disease such as diabetes), they are resistant to turnover, and can provide continuous protection against oxidation and inflammation.

Another critical function of the macular carotenoids involves their optical properties within the eye. Visual discomfort in glare (Stringham et al. 2004; Wenzel et al. 2006; Stringham & Snodderly, 2013), disability glare (Stringham & Hammond, 2007; 2008; Stringham et al., 2011; Hammond et al., 2013; Stringham et al. 2016), and photostress recovery time (Stringham & Hammond, 2007; 2008; Stringham et al., 2011; Hammond et al., 2013; Stringham et al. 2016) are all significantly improved with higher MPOD status. CS has also been found in several laboratories (for both normal and clinical populations) to be related to / enhanced by augmentation of MPOD (Kvansakul et al. 2006; Stringham et al. 2011; Sasamoto et al. 2011; Loughman et al. 2012; Yao et al. 2013; Nolan et al. 2017; Stringham et al. 2017). Dark adaptation speed, absolute scotopic thresholds, and mesopic contrast sensitivity have also been found to be impacted positively by MPOD (Hammond et al. 1998; Nolan et al. 2011; Patryas et al. 2013; Stringham et al. 2015).

A high concentration of macular carotenoids (i.e. high MPOD) is therefore advantageous in at least three ways: 1) Protection from oxidation and inflammation, 2) Filtration of potentially actinic high-energy short-wavelength light, and 3) Improvement of visual performance (via pre-receptor screening of short-wave light and neurophysiological enhancement). Importantly, the long-term protection conferred to the retina by the impressive antioxidant and filtering capability of MP translates to a significantly reduced risk of developing diseases that are brought on by cumulative tissue damage, including age-related macular degeneration (AMD; e.g. Seddon et al., 1994), the leading cause of blindness in the Western world (Klaver et al., 1998).

At baseline, our proposed study has the potential to determine cross-sectional relationships between MPOD, visual performance, and disease severity in glaucoma. Given the recent data from Siah et al. (2017), significant relationships are plausible – and if we determine these kinds of relationships, standard of care for glaucoma patients could be changed to include improved patient education regarding nutrition. Additionally, visual function testing (to include CS, DA, and DG testing) may be instituted for glaucoma suspects and established glaucoma patients. If we are able to show an acute effect of improvement in visual performance, disease parameters, or even simply increases in MPOD in glaucoma patients upon supplementation with macular carotenoids, it could lead to larger trials that may yield extremely important data with regard to management of glaucoma. Given the predicted exponential increase in worldwide glaucoma prevalence (76 million in 2020 to 111.8 million in 2040; Tham et al. [2014]), strategies that may delay the onset of visual disturbance or prolong good visual function would be hugely significant.

### **Study Design & Procedures**

The proposed study design is a randomized, double-masked, placebo-controlled one-year intervention in glaucoma patients with moderate to advanced disease. The total period of performance for this study (to allow for recruitment, experimental visits, analysis, and final report) would be 24 months.

#### **General evaluation:**

The following is a list of assessments to be conducted at each patient visit.

1. Measurement of MPOD. Equipment: The Heidelberg Spectralis with MPOD module will be used to obtain an MPOD spatial density profile; no dilation required. Patient time: 15 minutes.

**PI: [name], Ph.D**

2. CS testing. Equipment: M&S Technologies Smart System. Sine-wave gratings with frequencies of 1.5, 3, 6, 12, and 18 cycles / degree will be used to generate a contrast sensitivity function. Patient time: 15 minutes.
3. DG testing. Equipment: M&S Technologies Smart System with integrated glare testing system. Glare testing will be similar to the CS test, but only 6 cycles / degree will be assessed. Patient time: 10 minutes.
4. DA assessment. Equipment: MacuLogix Adapt Dx. Patients' speed of rod-mediated dark adaptation will be measured at 12o retinal eccentricity. This technology allows for rapid (< 10 minutes) assessment. Patient time: 10 minutes.
5. Visual Function Questionnaire (NEI VFQ-25). Patient time: 10 minutes.
6. Point-spread function; optical quality of the eye. Equipment: HD Analyzer. Patient time: 1 minute.
7. Visual field assessment. Equipment: SAP 24-2; SAP 10-2. Patient time (total): 15 minutes.
8. Review of medical history;

The results of the above assessments will be convolved with patients' clinical exam data to form the study's comprehensive database.

### **Selection of Subjects**

All participants must have signed the consent form. A power analysis based on previous retinal response and corresponding visual performance data from AMD patients revealed that 30 patients each in both placebo and treatment groups would be required to detect effects, if present. Assuming some attrition, we plan to recruit a total of 60 patients, half of which would be randomly assigned to receive a macular carotenoid supplement, containing 10 mg L, 2 mg Z, and 10 mg MZ (to be consumed once daily with a meal). In terms of macular carotenoid content, 22 mg total is roughly equivalent to 2 large bowls of spinach. The other half would receive an identical pill, containing only sunflower oil (as with the active supplement, patients would be instructed to take one pill daily, with a meal). Baseline measures (see below) for patients consenting to enroll in the study would be determined shortly after enrollment, prior to the onset of supplementation.

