### **Scheduled Visits**

Patients will be assessed at baseline, 3 months and 6 months (final visit).

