#### **Data Analysis & Statistical Considerations**

Baseline data will be analyzed with Pearson product-moment correlations, multiple regression, and (if clinically relevant group demarcation can be established, ANOVA). Intervention data will be analyzed primarily by repeated-measures ANOVA.

With our location in the Duke Eye Center, we foresee no issues in terms of patient recruitment or convenience for patient visits. Additionally, we have access to all of the experimental equipment (listed above) and other resources required to conduct the study.

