**PI: [name], Ph.D**

All statistical analyses will be performed by [name] and associates using commercially available statistical and mathematics software Stata (version 15; StataCorp LP, College Station, TX, USA), MATLAB (Mathworks, Inc.), and MPLUS (Muthen & Muthen). An alpha level will be generally set at 0.05, unless there is a need to correct for multiple comparison testing which will then be performed by procedures such as false discovery rate.

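### The plan requires 30 patients per group and recruits exactly 60 while saying it assumes attrition, so no attrition allowance is visible and the number needed at the final visit is not stated

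*Combined protocol and SAP*

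**What the plan says.** The only sample-size statement is in the combined protocol and SAP, Selection of Subjects. It reports that a power analysis, based on earlier retinal-response and visual-performance data in patients with age-related macular degeneration (AMD), "revealed that 30 patients each in both placebo and treatment groups would be required to detect effects, if present". The next sentence begins "Assuming some attrition, we plan to recruit a total of 60 patients", "half of which would be randomly assigned to receive a macular carotenoid supplement"; the other half receive placebo.

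The Data Analysis & Statistical Considerations section adds: "Intervention data will be analyzed primarily by repeated-measures ANOVA". On the significance level it says: "An alpha level will be generally set at 0.05", with correction for multiple comparisons if needed. Scheduled Visits lists baseline, 3 months and 6 months, the last being the final visit.

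The document gives no attrition rate, no number of patients expected or needed at the final visit, and no rule for replacing dropouts. It also does not state the power, effect size, SD or sidedness behind the figure of 30.

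**The concern.** The two sentences do not fit together on their natural reading. A number required to detect an effect is normally the number contributing data to the comparison. A recruitment target that takes attrition into account should then be larger than that number, and here it is the same.

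The placebo comparison is at stake. A reader cannot tell how many patients per arm it needs at the final visit, or whether 60 recruited patients can supply them. Repeated-measures ANOVA is named without a missing-data rule. In its classical complete-case form, a patient who misses one visit drops out of the analysis, so the evaluable number matters. The baseline cross-sectional aim is unaffected, because dropout comes after baseline.

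**Working it through.** **Inputs from the document.** Required: 30 per group. Recruited: 60, allocated 1:1. Alpha: generally 0.05. Visits: three. The power, effect size, SD, sidedness and attrition rate are not stated, so the 30 itself cannot be reproduced.

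**The total.** 2 x 30 = 60, which equals planned recruitment. The implied allowance is 1 - 60/60 = 0%.

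**Reading (a): 30 is the number needed with final-visit data.** Recruitment per arm would be 30/(1 - d), rounded up, for attrition d. All values of d are assumptions.

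| d | per arm | total | expected completers per arm if 60 are recruited |
|---|---|---|---|
| 5% | 32 | 64 | 28.5 |
| 10% | 34 | 68 | 27 |
| 15% | 36 | 72 | 25.5 |
| 20% | 38 | 76 | 24 |
| 25% | 40 | 80 | 22.5 |

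No rate in this range returns 60.

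**Reading (b): 30 already includes an allowance.** The evaluable number is then 30 x (1 - d): 27 per arm at 10% and 24 at 20%. The document states no such number.

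**What a shortfall would cost (illustration only).** Assume 80% power at 30 per arm and alpha 0.05, then reduce the evaluable number to 27 or 24 per arm.

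1. Group-by-visit test in a repeated-measures ANOVA with 2 groups and 3 visits, assuming sphericity, with incomplete patients removed. Degrees of freedom are 2 and 2(2n - 2), and the noncentrality is proportional to n. For 80% power at n = 30 the noncentrality is 9.89. At n = 27 it is 9.89 x 27/30 = 8.90, giving power 75.3%. At n = 24 it is 9.89 x 24/30 = 7.91, giving 69.7%.
2. Two-sided two-sample t-test, dropouts wholly lost. For 80% power at n = 30 the standardised difference is 0.736. Power is 75.6% at n = 27 and 70.4% at n = 24.
3. A model that keeps the 3-month data of dropouts: generalised least squares, compound symmetry, common baseline mean, normal approximation, every dropout leaving after month 3, visit correlation 0.5 to 0.9. The effective number per arm for the 6-month contrast is 27.3 to 27.6 at 10% loss and 24.5 to 25.1 at 20%. Power is 76.2% to 76.7% and 71.7% to 72.7%.

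If 90% power at 30 per arm is assumed instead, method 1 (noncentrality 12.99) gives 86.4% and 81.8%, and method 2 (standardised difference 0.851) gives 86.6% and 82.3%.

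**The case against.** The strongest reply is that this is ambiguous wording and not a proven arithmetic error. The text never says whether the 30 are randomised or completing patients. If attrition was already built into the 30, then 30 + 30 = 60 is consistent. That reading is possible. It changes the defect without removing it, because the evaluable number and the assumed rate are then undisclosed.

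A second reply is that no harm is shown. The 80% and 90% starting points and the 10% and 20% losses are assumptions. The 30 may have been rounded up or based on higher power; in the 90% illustration, power stays near 82% at 20% loss. The Benefits section also calls the study somewhat exploratory. All of this stands, and it limits the weight of the point. It does not justify wording that suggests an attrition margin the figures do not show.

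A third reply is that larger gaps come first. No primary outcome is named among the many listed under General evaluation, so a power figure has no defined target. The follow-up length is also unsettled: Study Design & Procedures describes a one-year intervention, while Scheduled Visits ends at 6 months. Both observations are right and bear on how the correction is completed. Neither makes the two sample-size sentences consistent.

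**Conclusion.** The concern holds and should be fixed. As written, recruitment equals the stated requirement, so no allowance is visible for the attrition that the plan itself assumes. The number needed at the final visit is not stated under either reading. This conclusion rests on the document's own figures and needs no assumption.

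The document does not show that 60 patients are too few. The size of any power loss depends on the assumed planning power, attrition rate and handling of incomplete patients. Over the cases examined (80% or 90% at 30 per arm, 10% or 20% loss), it is modest, roughly 3 to 10 percentage points, and it affects the intervention comparison only.

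**What to change.** Replace the two sentences with one statement filled in from the original power analysis, for example:

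> Sixty patients will be randomised, 30 per arm. With assumed attrition of [X]%, about [30 x (1 - X/100)] per arm are expected to have final-visit data. For that number, using the effect size [..] and SD [..] from the AMD data for [outcome] at [time point], power is [..]% (or the detectable difference is [..]) at [one/two]-sided alpha [..].

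State what the required 30 meant. If it meant randomised patients, say so and give the smaller evaluable number. If it meant patients with final-visit data, say plainly that 30 per arm are not expected from 60 recruited. In either case, remove the suggestion that 60 holds a margin over 30 per group. Reconcile the one-year and 6-month statements, since the assumed attrition depends on the length of follow-up.

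The cost is wording and retrieval of the original effect size and SD; no extra patients are needed. If 30 was the number needed for the comparison, the reported power will be slightly less favourable than one computed at 30 per arm. Raising recruitment to keep 30 evaluable per arm is optional and not needed for this correction. It would mean 68 patients at 10% loss or 76 at 20%, that is, 8 or 16 more.

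### Neither the allocation nor the intervention analysis uses disease severity, although the sample spans moderate to advanced glaucoma and a baseline visual field is already scheduled: a modest loss of precision and credibility, not a bias

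*Combined protocol and SAP*

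**What the plan says.** Study Design & Procedures describes the population as "glaucoma patients with moderate to advanced disease". Selection of Subjects states that "we plan to recruit a total of 60 patients", "half of which would be randomly assigned to receive a macular carotenoid supplement", and that "The other half would receive an identical pill, containing only sunflower oil". It names no stratification factor, block scheme or way of generating the sequence.

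Item 7 of the assessments made at every visit is "Visual field assessment. Equipment: SAP 24-2; SAP 10-2". Selection of Subjects places the baseline measures after enrolment and before supplementation starts. Scheduled Visits gives baseline, 3 and 6 months.

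Data Analysis & Statistical Considerations says: "Intervention data will be analyzed primarily by repeated-measures ANOVA". It does not say whether baseline is a level of the repeated factor, which effect is the treatment test, or whether any covariate is used. Regression, and ANOVA if clinically relevant groups can be formed, are planned for the baseline cross-sectional data only.

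The documents do not define moderate or advanced, do not give the expected mix, and name no study eye. The inclusion and exclusion criteria set no severity limit.

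**The concern.** The protocol itself expects vision to depend on disease. Background & Significance describes visual function deficits in glaucoma and reports a study in which low carotenoid levels went with glare problems and greater ganglion cell loss. It also makes the relation of macular pigment and visual performance to disease severity a baseline aim. Severity is therefore a likely predictor of contrast sensitivity, glare, dark adaptation and the questionnaire.

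With 30 per arm, one arm may by chance hold noticeably more advanced patients. Readers would then question a positive or a null result, and any analysis that compares follow-up levels would carry avoidable noise. The measurement that would address this is already scheduled and costs the patient nothing more. Stratification, unlike a covariate, cannot be added once allocation has started.

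**Working it through.** **The plan's own figure.** The protocol says "30 patients each in both placebo and treatment groups would be required to detect effects, if present". This cannot be reproduced, because effect size, SD and power are not stated. Solved backwards, assuming two-sided 0.05 and 80% power, 30 per arm detects (1.960 + 0.842) × √(2/30) = 0.72 SD, or 0.74 SD with the t distribution. This serves only as a yardstick.

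**Chance of imbalance.** From the protocol: N = 60, half to each arm. Assumed: arms fixed at 30/30 and K advanced patients in total. The number of advanced patients in the active arm, X, is hypergeometric (60, K, 30), and the arms differ by |2X − K|.

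| Advanced, of 60 | Differ by ≥ 6, either direction | Differ by ≥ 8 |
|---|---|---|
| 30 | 19.6% | 7.0% |
| 24 or 36 | 18.7% | 6.4% |
| 20 or 40 | 17.0% | 5.4% |
| 12 or 48 | 10.4% | 2.1% |

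An even mix gives the largest of these values. The chance of six or more extra advanced patients in one named arm is half the figure, 9.8% at K = 30.

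**What an 18 v 12 split does.** The proportions differ by 18/30 − 12/30 = 0.2. Assume advanced patients score p SD lower, equally at baseline and follow-up, with p = 0.5 to 1.5 and SD 1 within severity group.

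- Follow-up values alone: shift 0.2p, so 0.1 to 0.3 SD.
- Change from baseline, or group-by-time with baseline as a level: the constant p subtracts out within each patient, so the shift is 0.
- Own baseline as covariate: shift 0.2p × (1 − c/s²). Here s² = 1 + q(1−q)p², c = ρ + q(1−q)p², q is the advanced fraction and ρ the within-group retest correlation. For p = 1, ρ = 0.6, q = 1/2: 0.2 × (1 − 0.85/1.25) = 0.064 SD. Over p = 0.5 to 1.5, ρ = 0.4 to 0.8 and q = 1/2 or 1/3, the range is 0.02 to 0.12 SD.

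**Precision.** Residual variance is 2(1 − ρ) for change, s² − c²/s² with own baseline, and 1 − ρ² with own baseline plus severity. At q = 1/2:

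| p, ρ | Change | Own baseline | Plus severity | Cut from severity |
|---|---|---|---|---|
| 0.5, 0.8 | 0.40 | 0.362 | 0.360 | 0.6% |
| 1.0, 0.6 | 0.80 | 0.672 | 0.640 | 4.8% |
| 1.5, 0.4 | 1.20 | 0.970 | 0.840 | 13.4% |

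In patients, the severity term is worth 60 × (0.362/0.360 − 1) ≈ 0, up to 60 × (0.970/0.840 − 1) ≈ 9.

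**Simulated power.** N = 60, true effect 0.6 SD, q = 1/2, one follow-up value, unstratified allocation; simulation error is up to about a point.

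| Analysis | p = 1, ρ = 0.6: without → with severity | p = 1.5, ρ = 0.4: without → with severity |
|---|---|---|
| Change from baseline | 73% → 73% | 55% → 54% |
| Own baseline as covariate | about 80% → 80% | 64% → 69% |
| Follow-up level only | 54% → 63% | 45% → 62% |

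With both covariates in the model, stratifying the allocation as well moves power from 80.2% to 80.9% and from 68.9% to 69.3%.

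**The case against.** The strongest objection is that repeated-measures ANOVA with visits at baseline, 3 and 6 months is usually read as a group-by-time test. A severity difference that stays constant then cancels within patients however the arms split, and a severity term gains nothing. This stands under that reading, and the simulation confirms it. It does not settle the matter, because the plan does not say that baseline is a level or which effect is tested. A group main effect or a follow-up comparison would not cancel the difference. Severity that predicts the rate of change would not cancel either, and the documents give no figure for that.

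It can also be said that randomisation protects the type I error whatever imbalance occurs, and that stratifying a 60-patient study that calls itself somewhat exploratory is a matter of preference. Both are fair. They limit the point to precision and credibility, and make stratification optional.

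A reader might infer a flat one-in-five risk that one arm is favoured on every visual outcome. The documents do not support that. The probability needs a severity mix that is nowhere stated, it counts both directions, and the shift depends on a treatment test that is not specified. Nor do they show that allocation will be unblocked; the method is simply not described.

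**Conclusion.** The point holds as a modest, optional improvement. No severity stratum is named in the allocation and no severity term in the intervention analysis, although a baseline field is already collected. The 17% to 20% figure for a difference of six or more assumes fixed 30/30 arms and between one-third and two-thirds advanced.

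The cost depends on the analysis: nothing for group-by-time under stable severity, a small amount for a baseline-adjusted model, and most for a comparison of follow-up levels. The severity effects and retest correlations behind these sizes are assumptions, since the documents give neither. It would go too far to conclude that the planned test is biased or invalid, or that the plan as written is shown to lose precision for want of a severity term.

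Against a change analysis, most of the gain comes from adjusting for the outcome's own baseline. At p = 1 and ρ = 0.6, that step takes residual variance from 0.80 to 0.67, and severity takes it on to 0.64.

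**What to change.** **Data Analysis & Statistical Considerations (main change).** State that the 3- and 6-month values of each outcome will be compared between arms in a repeated-measures model, with the outcome's own baseline and continuous baseline 24-2 mean deviation as covariates. Name the treatment contrast. Say which eye supplies the mean deviation (the study eye, or a rule fixed in advance for patients whose eyes differ). Where 24-2 mean deviation is itself the outcome, the two covariates are the same. The cost is one degree of freedom for severity and no new procedure.

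**Selection of Subjects (optional).** Randomise after the baseline field, in permuted blocks within two mean-deviation strata whose cut-off is fixed before enrolment. With blocks of four, for example, the advanced counts cannot differ by more than 2, so a six-patient imbalance cannot occur. The costs are two lists instead of one, allocation that waits for a test already scheduled, arm totals that may differ slightly if blocks are left incomplete, and the need to define moderate and advanced. Once the covariate is used, this adds only about one point of power; its value is in balance and credibility.
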